Participants will utilize the STAMP+CBT app for 4-weeks (intervention study period). The 4 weeks will consist of all content introductions. STAMP+CBT hosts and organizes patients' opioid/non-opioid analgesics. It has an extensive multi-media library of education content related to pain management (Appendix A) and pain specific CBT concepts (Appendices A, L, and G). Content will be delivered on a schedule to ensure that patients receive all pain CBT and medication education available (Appendix B). STAMP+CBT prompts patients to take daily surveys to report their pain, pain catastrophizing, mood, opioid/pain medication use, and sleep symptoms and progress towards individualized goals (Appendix B). At the end of each survey, patients receive feedback according to their symptom severity, with links to tailored educational content about pain and psychological symptom management (Table 2, Appendix B). Patients also complete weekly surveys for reporting symptoms listed above as well as goal progress.

If patients report any severe symptoms (Table 3), they are instructed to contact their care team immediately, with a telephone number included on the application screen, see table 2, or to go the Emergency room/call 911 for a true medical emergency. If patients' pain is poorly controlled but not severe enough to be prompted to immediately contact their care team (for example if their average pain is above a 4 and not acceptable), they are reminded to contact their care teams if their symptoms worsen or if they are concerned about it.

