One protocol-mandated study staff outreach to patients will occur within a week of enrollment. A study team member will call to assess any technical or usability problems with the app (e.g., how to access the app on their phone, where to find certain study areas). These technical discussions will be optional for the patient and more can be scheduled if requested. Thereafter, the study team member will monitor the STAMP+CBT dashboard twice daily (Mon-Fri) to assess app engagement and survey completion rates (Table 3). If a patient reports one of these severe symptoms, the app sends an automated email to the research team listing patients concerning symptoms. (See Table 3). A member of the research team will then forward a copy of the patients concerning symptoms to their study nurse for evaluation or follow-up. As an additional safety measure, the application always prompts the patients to contact their care team or 911 for any severe symptoms they report and there is no expectation for proactive clinician outreach. These procedures have been approved by participating clinic nurses. The application provides a direct link to call the Outpatient Supportive Care Clinic at OUHSC.

To minimize the burden of the intervention on clinicians, patients are prompted to call their care teams or 911 (emergency services) if they report severe symptoms (Table 3). Patients are reminded during onboarding to the app that the research portal is not monitored around the clock and therefore they should reach out for urgent needs. Reports (with summarized pain and psychological symptoms; opioid use data; side effects; patients' goals and reported goal attainment) will be sent from a study team member to nurse managers, supportive care providers, and oncologists to enable effective communication, opioid titration, and other management changes when alerted by a patients red flag symptom email via in-app algorithms.

During the study, patients will be asked to complete 3 survey assessments, one at baseline, one at the end of the 4-week intervention period, and another at the end of the 2-week post intervention period. Patients will also be invited to complete a short semi-structured interview about their experiences using the application (See Appendix T). See below for description of the surveys (Table 4).

Table 2: Algorithms used to provide feedback to patients

Relief with opioids	No relief OK Unsure
---------------------	---------------------------

	Good relief

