Pain Control	Poor Suboptimal Good
Other Severe Symptoms	Number of severe symptoms on Table 2
Opioids need updating	Yes No
Mood	IF Patient responds to mood questions 17-20 with a total score of ≥ 12 : Low Mood IF Patient responds to mood questions 17-20 with a total score of < 12 : High Mood
Catastrophizing	IF Patient responses to catastrophizing questions 12-16 with a total score greater than ≥ 10 : High Stress IF Patient answers catastrophizing items 12-16 with a total score < 10 : Low Stress
Sleep	If sleep item 23 on the survey score ≥ 3 : Poor If score < 3 : Good
Goals need updating	IF Patient answers “No, it needs to be changed” in goal-setting section of weekly survey: Goal needs updating

Table 3. Severe Symptoms that trigger an email alert to the research team

Pain	
 • Worst pain = 9-10 • Worst pain = 7-10 and new pain
Red Flag Symptoms	
 • Severe weakness or fatigue • Lightheadedness or feeling like I was going to pass out • No gas or stool from my bottom (or ostomy) in the last 2 days • Vomiting 2 or more times in the last 24 hours • Fever of 100.5 or greater • New or worsening chest pain • New or worsening shortness of breath • New or worsening back pain • New numbness and weakness in one or both of your legs • Severe difficulty eating or drinking • Hallucinations/nightmares
Opioid Side Effects	
 • Hallucinations

STUDY TIMELINES

Patients in this Pilot Cohort will be in the research study for 6 weeks total including: a 4-week intervention period and 2-week post intervention period. Patients will use the app for a total of 4 weeks and remain on study through the 2-week post intervention period. They will complete surveys at baseline, 4 weeks (end of intervention period), and at 6 weeks (end of 2-week post intervention period).

We anticipate enrolling 1-2 patients per week during the pilot period, and should this complete the study within 6-8 months.

The study timeline may change due to unforeseen circumstances. The estimated date for the investigators to complete this study (complete primary analysis) is July, 2024.

E. Chart Review

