As such, the only adverse event that will be monitored and reported is psychological distress as determined by the treating clinician. For any patient who exhibits severe distress as result of the study procedures, the study research assistant will notify the patients' clinician and social worker for appropriate response, including possible mental health referral if necessary. Patients' scores on self-administered assessments (e.g., pain score, mood) within the app will be used to determine if an adverse event has occurred. In these instances, an email alert will be automatically sent to the study team describing the patient's severe symptoms. Study staff will report the patient's symptoms by forwarding the email to the patient's care team, who will then contact the patient for further information. The alert will also instruct patients to contact their care team or call 911. Patients have immediate access to study staff through a call button on the app's home screen and will be advised to call research staff for any severe adverse events or other study-related needs, which will then be communicated with the clinical team when necessary and reported to the IRB. Any severe adverse event that is related to the physical and psychological risks described below and that results from participation in the study will be reported to the IRB within 2 business days and to the NIH within 5 business days. Furthermore, participants will be reminded that participation is voluntary and can be stopped at any time for any reason.

Recruitment and Informed Consent: Participants will only be approached if approval is received by their treating clinician. If the physician deems them unsuitable for the study, they will not be approached. Participants will be approached in clinic or by phone by a study team member in a private and confidential manner. If the patient is eligible and interested in participation, the study letter, consent and HIPAA form (Appendices AD, W, and Y) will be reviewed with the participant.

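### Section K says in-app mood scores lead to an automatic staff email, but Table 3, the list of email triggers, contains no mood or distress score

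*Combined protocol and SAP*

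**What the plan says.** Section K, Risks and Risk Mitigation, states that "the only adverse event that will be monitored and reported is psychological distress as determined by the treating clinician". It then says how such an event is picked up: patients' "scores on self-administered assessments (e.g., pain score, mood) within the app will be used to determine if an adverse event has occurred". When that happens, "an email alert will be automatically sent to the study team", and staff forward it to the care team.

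Section D, Intervention, says which reports produce the automatic email and refers to Table 3, titled "Severe Symptoms that trigger an email alert to the research team". Table 3 has three groups: pain, red-flag symptoms and opioid side effects.

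Table 2 sets out the algorithms for feedback to patients and holds the psychological cut-offs:
- Mood: "IF Patient responds to mood questions 17-20 with a total score of" 12 or more, classed as low mood.
- Catastrophizing: "IF Patient responses to catastrophizing questions 12-16 with a total score greater than" or equal to 10, classed as high stress.

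Two further steps in Section D rest on the same list or the same email. On the patient side, "If patients report any severe symptoms (Table 3), they are instructed to contact their care team immediately". On the clinician side, summary reports that include psychological symptoms go out "when alerted by a patients red flag symptom email via in-app algorithms".

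**The concern.** Section K names mood as one of the scores that decide whether the event has occurred and start an email. The list that defines the email does not include it. Someone programming from Table 3 would build no mood alert. Someone programming from Section K would know that one is needed but would find no alert threshold.

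At stake is the score-based screen for the one event that this part of Section K says is monitored. The treating clinician, who is to judge distress, would not be sent a severe mood score unless the patient also reported a listed symptom. Section K also says the app watches psychosocial needs more closely than usual care does, and it acknowledges that patients who feel monitored may be less inclined to call. Both statements make it important that the promised alert exists.

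**Working it through.** The protocol gives no figure to reproduce here. The check is a count of Table 3 and a comparison of the sections.

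**1. Count of email triggers (Table 3).**

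| Group | Entries | Mood or distress score |
|---|---|---|
| Pain | 2 | 0 |
| Red-flag symptoms | 11 | 0 |
| Opioid side effects | 1 | 0 |
| Total | 2 + 11 + 1 = 14 | 0 |

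Hallucinations appear in two groups, so there are 14 - 1 = 13 distinct triggers. The nearest psychological item is the hallucinations/nightmares entry, which is a symptom report and not a mood score. No entry refers to mood, stress, distress, depression, anxiety or catastrophizing. The examples in Section K, Protection against physical risks, which point to Table 3 for detail, are also all physical.

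**2. Which text links mood to an action.**
- Section K: mood score leads to an email to staff. No cut-off is given.
- Table 2: mood total of 12 or more leads to patient feedback. No staff email is attached.
- Table 3: staff email. No mood entry.

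No section supplies both the mood cut-off and the staff email.

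**3. Whether another step closes the gap.**
- The instruction to contact the care team immediately is tied to Table 3.
- The reports to clinicians follow a red-flag email.
- The twice-daily weekday dashboard checks (Section D) are described as being for engagement and survey completion.

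None of these sends a severe mood score to staff when no listed symptom is reported.

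**4. What a total of 12 means.** Four items totalling 12 average 12/4 = 3 per item. The item scale would be in Appendix B, so the position of 12 within the score range has to be shown under assumed scales:
- items 0-4: 12/16 = 75% of the range
- items 1-5: (12 - 4)/(20 - 4) = 8/16 = 50%
- items 0-10: 12/40 = 30%

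So 12 could mark fairly severe low mood or fall at or below mid-scale. The alert cut-off has to be checked against the actual scale.

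**The case against.** The strongest reply is that distress has other routes to attention. Section C describes feedback on mood that can include advice to contact the care team. Section K provides a call button, notification of the clinician and social worker when a patient shows severe distress from study procedures, and referral when a patient raises distress. The event is also the clinician's judgement, so a low mood score in advanced cancer is at most a screen. All of this stands, and it narrows the consequence. It does not supply the staff email that Section K describes.

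Second, Section D refers the survey and feedback logic to Appendix B, which may contain a mood alert. Table 3 is also not a flawless authority: Section K cites it for any new pain and for pain of 8 or more, whereas Table 3 lists 9-10, or 7-10 with new pain. A reader might infer that the app has no mood alert at all. The documents show only that the stated rules disagree.

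Third, the plan deliberately limits clinician burden, so the sponsor may not want a mood alert. That is a legitimate choice, but Section K would then need to say so.

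Three other stronger readings should be resisted:
- A reader might infer that no other adverse event is reported. Section M provides for reporting of all adverse events, with serious ones reported within 2 working days.
- A reader might extend the gap to the REDCap surveys. Section K limits score monitoring to the app. Staff meet the patient after the baseline survey and contact participants at weeks 4 and 6, and the survey appendices are not available here.
- A reader might want a number of missed events. The documents give no rate of severe mood scores, so none can be derived.

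**Conclusion.** The point holds as an internal inconsistency in safety monitoring. Section K promises a staff email based on scores that include mood, while 0 of the 14 entries in Table 3 (13 distinct) is a mood or distress score. The existing mood cut-off serves patient feedback only.

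The consequence is conditional. If the alerts are programmed from Table 3 as written, a severe mood score without a listed symptom reaches neither staff nor the treating clinician through the alert system. The gap is in the score-based route, not in all detection of distress. The conclusion assumes that Table 3 is the complete list of email triggers, as its title and Section D present it, and that Appendix B does not add a mood rule. If Appendix B does add one, the remaining fault is that Table 3 is incomplete. The primary feasibility endpoint and the precision calculation are unaffected. The sponsor should resolve this.

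**What to change.** Add one row to Table 3: mood, total of questions 17-20 at or above 12. If the Appendix B item scale puts 12 at mid-scale or lower, fix a higher severe cut-off from that scale instead. Send and forward this alert in the same way as the others. If Appendix B already holds a mood alert, copy its cut-off into Table 3.

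The cost is one app rule on a score already computed and a short amendment. The downside is extra alerts for staff to forward. Their number is unknown, and a low cut-off could make it large, which is why the scale check comes first.

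If the sponsor intends no mood alert, remove mood from the Section K sentence on in-app scores and qualify the statement under Protection against psychological risks about closer psychosocial monitoring. This restores consistency at almost no cost, but it leaves distress without a score-based alert.

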Participants may feel reassured that their symptoms are being monitored and be less likely to call their care team. We have sought to mitigate this possibility in multiple ways. First, study staff emphasize and reiterate that the study platform is not monitored continuously during onboarding. Staff tell participants to contact their care team or call 911 should any concerning symptoms arise. Second, when patients report potentially serious symptoms, they are specifically instructed by the application to notify their care team by calling or paging after hours (the clinic number is included in the application). See Table 3 for the list of symptoms that prompts phone contact.

Protection against psychological risks: If in the course of their participation patients raise significant emotional distress, the appropriate care team members (i.e. nurse navigator, physician, mid-level provider) will be contacted to make appropriate social work or mental health referrals. Similar to that of physical

risks, this app provides closer monitoring than what is provided for usual care for psychosocial needs.

Benefits and knowledge to be gained: Using the STAMP+CBT app and taking part in this research study may or may not benefit participants. We hope that by reviewing the content in the STAMP+CBT app, patients are able to better manage their symptoms and the increased flow of information between a patient and their care team improves their experiences. We also hope the information learned from this research study will provide more information about how patients' pain management experience varies between clinic visits, as at-home app management will allow for increased monitoring of system and therefore increased access to daily symptom data. Lastly, we hope this will help patients and their care team work together during and between visits to achieve better symptom management in cancer patients.

L. Statistical Methods

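### Section K advises patients to call research staff for severe adverse events, other text sends severely unwell patients to the care team or 911, and the protocol does not say how the two calls relate

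*Combined protocol and SAP*

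**What the plan says.** Section K, under Risks and Risk Mitigation, describes a route to the research team: "Patients have immediate access to study staff through a call button on the app's home screen". Patients "will be advised to call research staff for any severe adverse events or other study-related needs". What they report is then passed on to clinicians if that is needed, and the IRB is informed.

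The other statements on whom a severely unwell patient should contact point to clinical care:

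- Section D, Intervention: a patient reporting a severe symptom is told to contact the care team at once, using a number shown on the screen, or to use the emergency room or 911 in a true emergency. Also, "the application always prompts the patients to contact their care team or 911 for any severe symptoms they report".
- Section D, Intervention, on the telephone link: "The application provides a direct link to call the Outpatient Supportive Care Clinic at OUHSC".
- Section K, in the same paragraph as the research-staff advice: the alert directs patients to the care team or 911.
- Section K, Protection against physical risks: the app is said always to direct patients to their care teams, here without mention of 911. Further on, onboarding staff advise the care team or 911 for concerning symptoms, and for potentially serious symptoms "they are specifically instructed by the application to notify their care team by calling or paging after hours".

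On staffing, Section D gives one schedule: dashboard checks twice daily, Monday to Friday, to follow engagement and survey completion. Patients are told at onboarding that the research portal is not watched continuously.

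**The concern.** A patient cannot be expected to separate a severe adverse event, for which Section K names research staff, from a severe symptom, for which the rest of the protocol names the care team or 911. If the Section K advice is followed as written, the first call may go to a research team that then decides whether the clinical team needs to know. The text sets no time limit for that step and does not say when the line is answered.

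The participants have advanced cancer and are prescribed opioids. The severe symptoms in Table 3 include new or worsening chest pain, fever, and new leg numbness and weakness. The protocol itself recognises, under Protection against physical risks, that patients who feel monitored may be less inclined to call their care team. Promising immediate access to study staff, and advising patients to use it for severe events, works against the mitigation described there.

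**Working it through.** No sample-size, power or error-rate figure bears on this point and the plan states no figure to reproduce. The check is a comparison of the text in four steps.

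**1. Do the two instructions cover the same episodes?** They can. Section K says "Patients' scores on self-administered assessments (e.g., pain score, mood) within the app will be used to determine if an adverse event has occurred". The in-app report that triggers the care-team prompt can therefore also be what makes the episode an adverse event. Section K does not define a severe adverse event. The nearest definition, for serious adverse events in Section M, includes life-threatening events and hospitalisation, so the research-staff advice cannot be assumed to concern only minor matters.

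**2. Is there an order, or a limit on purpose?** None is stated. Section K places the care-team or 911 instruction and the research-staff advice close together without linking them. No section says that the clinical call comes first, that the staff call is additional, or that it serves reporting only. The mention of the IRB suggests a reporting purpose. The mention of passing information to clinicians when necessary suggests that the staff call may also be how the clinical team learns of the event.

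**3. Is immediate access supported?** Not in the available text. Neither Section D nor Section K gives hours or an on-call arrangement for the staff line. The Monday-to-Friday schedule is for the dashboard, so it neither supports nor contradicts telephone cover. After-hours contact is described only for the care team.

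**4. What do the call features dial?** Section K describes a home-screen button to study staff. Section D describes an on-screen number for the care team and a link to the supportive care clinic. Section K also mentions a link to the care team's number. These can be separate features, but the protocol never sets them out together or says how a patient tells them apart.

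| Situation | Whom the patient is told to contact | Availability stated |
|---|---|---|
| Severe symptom reported in the app (Sections D and K) | Care team; 911 or emergency services in all but one description | Calling, or paging after hours |
| Concerning symptom (onboarding, Section K) | Care team or 911 | Not specified |
| Severe adverse event (Section K) | Research staff, who inform clinicians when necessary | Immediate access; no hours given |

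**The case against.** The strongest reply is that the instructions add to one another. The care-team or 911 instruction stands beside the research-staff advice, which also covers other study needs and mentions the IRB. It can be read as an event-reporting and support line, and nothing tells patients to call staff instead of, or before, a clinician. Onboarding teaches care team or 911, the app repeats it, and after-hours paging is described. This stands: the instructions do not exclude each other, and patients do have an emergency route. It does not supply the missing statement of how the calls relate.

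Three stronger readings are tempting, and the documents do not support them:

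- A reader might infer from the Monday-to-Friday schedule that the staff line is unanswered at weekends and at night. That schedule describes dashboard checks. Telephone cover is unstated, which is not the same as absent, so no proportion of uncovered time can be calculated.
- A reader might infer that a single in-app call function is described in two incompatible ways. The home-screen button and the clinic link may be different features.
- A reader might infer that onboarding staff could teach either route. Section K says what they teach: care team or 911.

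Appendix S (onboarding and monitoring) and Appendix AD (consent form) are not in the available text. They may give the order of calls and the hours of the line. Their absence here is not a fault in the plan.

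**Conclusion.** The concern holds as an unreconciled safety instruction. For a severe event, Section K names research staff while Section D and the rest of Section K name the care team, mostly with 911. One episode can meet both descriptions, and neither the order nor the purpose of the staff call is stated. The promise of immediate access has no stated hours behind it.

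The size cannot be put as a number. The wording reaches every app user, up to 60 patients. Delayed help is a possible consequence, and the repeated care-team and 911 instructions reduce its likelihood; the documents do not demonstrate it. The conclusion rests on the protocol body alone and assumes that Appendices S and AD do not already settle the matter. If they do, the protocol body still needs to match them. Because the instruction concerns severely ill patients and the repair is small, it should be corrected.

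**What to change.** Reconcile Section D (Intervention) with Section K (Risks and Risk Mitigation, and Protection against physical risks):

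1. State explicitly, for severe symptoms and severe adverse events, how the call to research staff relates to the call to the care team or 911: its order and its purpose. The sponsor and clinic must decide the route.
2. State what the home-screen button and the clinic link each dial, and check these against the numbers programmed in the app.
3. Either give the hours of the research-staff line or remove the claim of immediate access.
4. Check that the onboarding material (Appendix S) and the consent form (Appendix AD) say the same.

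The cost is protocol wording, a check of two appendices and a check of the app's numbers. Removing the immediacy claim needs no extra staff; keeping it means stating cover that exists or arranging it. Sample size, endpoints and analysis are unaffected.

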In the case of remote approach by phone, a study team member will attempt to contact the patient 3 times. If the patient contact cannot be established, the study team member will email a copy of the recruitment letter to the patient (Appendix AC). The recruitment letter encourages the patient to reach out to the study staff if they are interested in participating. If a patient reaches out to the study staff then the study letter, consent form, and HIPAA authorization form (Appendix W) will be reviewed before the patient provides written consent. During remote approaches by phone the study letter, consent and HIPAA forms will be sent by email through a secure and personalized link in REDCap. While discussing the study letter and consent the study staff will emphasize that participation is voluntary and the participant may stop participating at any time. Consent discussions may take place over the phone or HIPAA-compliant Zoom.

Protection against physical risks: The study team has placed extensive protections against the aforementioned physical risks of the app which have been approved in the initial app protocol (DF/HCC #18-504). These protections significantly exceed the level of support and guidance that patients would receive with usual care. Finally, the patient-facing app always instructs patients to contact their care teams and reminds them that the research portal is not monitored continuously.

The STAMP+CBT application sets a low bar for instructing patients to contact their care teams for reported symptoms. This includes reporting any new pain, fever, new or worsening back pain, new or worsening chest pain, any pain rated ≥ 8 out of a 0 to 10 scale (See table 3 for the detailed list). Moreover, if patients report moderate to severe pain levels that do not meet the previous criteria, in addition to receiving education about their pain management, they are also reminded that their care team wants to hear from them if they are concerned about their symptoms or if their symptoms are not improving. A link to their care team's number is included in the application. This level of support is much greater than what patients have usually with routine care.

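### The safety text contradicts itself on which pain reports prompt patient contact, whether app mood scores raise an alert, which adverse events are reported, and whether clinicians contact the patient after an alert

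*Combined protocol and SAP*

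**What the plan says.** **Pain triggers.** Section K (Protection against physical risks) says of the reports that lead to an instruction to contact the care team: "This includes reporting any new pain, fever, new or worsening back pain, new or worsening chest pain, any pain rated ≥ 8". It refers to Table 3 for the detail. Table 3 in Section D has two pain entries: worst pain of 9-10, and "Worst pain = 7-10 and new pain". Its caption makes it the list for email alerts to the research team, but other text also makes it the patient-contact list. Section D (Intervention) says "If patients report any severe symptoms (Table 3), they are instructed to contact their care team immediately", and Section K says "See Table 3 for the list of symptoms that prompts phone contact".

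**Mood alert.** Section K (Risks and Risk Mitigation) says that app scores, with pain and mood as examples, "within the app will be used to determine if an adverse event has occurred". It continues: "In these instances, an email alert will be automatically sent to the study team". The mood cut-off is in a different table, captioned "Table 2: Algorithms used to provide feedback to patients".

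**Adverse event scope.** Section K says "the only adverse event that will be monitored and reported is psychological distress as determined by the treating clinician". The same paragraph then sets reporting times for severe adverse events that result from participation: 2 business days to the IRB and 5 to the NIH. Section M sends every adverse event to the IRB and the investigators. It also sets 2 working days (IRB and investigators) and 5 business days (NIH) for serious adverse events, with no condition that they be related to the study.

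**Contact after an alert.** Section K says the care team, on receiving the forwarded email, will contact the patient. Section D (Intervention) says the alert goes to the study nurse for evaluation or follow-up, and that proactive outreach by clinicians is not expected.

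**The concern.** Section K is the protocol's account of how risk is controlled, and in places it describes more protection than the operational text in Section D provides. If the app is built to Table 3, some patients who according to Section K are told to contact their care team will not be told. Where their pain is poorly controlled, or moderate to severe, but below Table 3's triggers, they get a conditional reminder instead. The automatic mood-score alert has no entry in the list that defines alerts.

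The adverse event text leaves staff with two reporting scopes. Section E (Chart Review) expects that some patients may die during the study. A death unrelated to participation falls under the clocks in Section M but not under those in Section K. Nor can staff tell whether a clinician is expected to call after an alert. Section K itself recognises that patients may feel monitored and so be less likely to call.

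**Working it through.** The plan gives no figure of its own to reproduce here. The pain rules can be enumerated; the other three points are comparisons of text.

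**1. Pain triggers**

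Inputs: pain score 0-10 and whether the pain is new. The comparison treats Section K's pain rating and Table 3's worst pain as the same score.

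- Section K rule: new, or score ≥ 8.
- Table 3 rule: score ≥ 9, or score ≥ 7 and new.

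Leaving out new pain at score 0, there are 11 combinations for pain that is not new (0-10) and 10 for new pain (1-10), so 21 in all.

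| | Not new | New | Total |
|---|---|---|---|
| Combinations | 11 | 10 | 21 |
| Section K triggers | 3 (8, 9, 10) | 10 (1-10) | 13 |
| Table 3 triggers | 2 (9, 10) | 4 (7-10) | 6 |
| Section K only | 1 (score 8) | 6 (1-6) | 7 |
| Table 3 only | 0 | 0 | 0 |

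If new pain at score 0 is counted literally, there are 22 combinations: Section K 14, Table 3 6, difference 8. New or worsening back or chest pain is a red flag in Table 3 at any score, so the gap concerns pain elsewhere.

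**2. Mood alert**

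Table 3 has 2 pain entries, 11 red flag symptoms and 1 opioid side effect: 2 + 11 + 1 = 14. None is a mood or distress score. Table 2 classes a mood total of 12 or more as low mood, under a caption about feedback to patients. Section K also says both that distress is determined by the treating clinician and that app scores determine whether an adverse event has occurred.

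**3. Adverse event reporting**

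| | Section K | Section M |
|---|---|---|
| Events reported | Distress only, then also severe adverse events | All adverse events |
| Events on the 2- and 5-day clocks | Severe, and resulting from participation | All serious adverse events, related or not |
| Term defined | Severe: no | Serious: yes, including death and hospitalization |

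The day counts agree. The events to which they apply do not.

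**4. Contact after an alert**

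Section K commits the care team to contacting the patient. Section D disclaims any such expectation. The nurse's evaluation or follow-up in Section D does not amount to the commitment in Section K.

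**The case against.** The best defence on pain is that the rules are nested: every Table 3 pain trigger is also a Section K trigger. An app could instruct patients on the broader list and email staff on the narrower one. Table 3's caption supports this, and Section D does not say that only Table 3 symptoms lead to an instruction. The nesting is correct. But Section K cites Table 3 as the detail of its own list and as the list that prompts phone contact, so on that reading those cross-references are wrong. The text still needs correcting, and the app's behaviour is still uncertain.

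On mood, the defence is that mood is only an example in brackets, and that Table 2's caption does not prove its items never reach staff. Section D describes a survey item that notifies the team when a medication or goal needs changing, and Table 2 contains related rows. Appendix B, which holds the survey and algorithms, is not among the documents reviewed, so what the app does cannot be confirmed. Distress can also reach staff through clinician judgement, or when a patient shows or raises it. All of this stands. What remains is an automatic alert described in Section K that is missing from the protocol's stated alert list.

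On adverse events, a clock on a subset does not by itself contradict a wider clock, and severe and serious are different terms. That is fair for the clocks taken alone. It does not rescue the statement that distress is the only event reported, which cannot stand beside Section M.

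Finally, there are backstops: reminders, a phone link, weekday dashboard checks, and advice at onboarding to call the care team or 911. They lessen the possible harm but do not settle which instruction applies.

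**Conclusion.** The concern holds on all four points, and the text must be reconciled. The pain rules differ in 7 of 21 score combinations (8 of 22 if new pain at score 0 is counted). In each of these Section K prompts contact and Table 3 does not. No mood or distress score appears among Table 3's 14 entries. The adverse event scope and clinician contact after an alert are stated in incompatible ways.

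The counts assume that the two pain ratings are the same score and that newness is a single yes or no. They are combinations, not patients or alerts; the documents give no score frequencies, so the number of people affected cannot be estimated. Confidence is high about the conflicts in the text, but how the app is actually programmed is unknown. The harm is to patient protection and consistent adverse event reporting. The feasibility and acceptability results are unaffected.

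**What to change.** - Have the clinical investigators settle one list of triggers, and make Table 3, Section D, Section K and the app logic agree with it. If patient prompts and staff emails are meant to use different lists, label each and correct the cross-references.
- Either enter the score-based distress alert in Table 3 or remove the statement in Section K that one is sent.
- State one adverse event reporting scope, with one set of defined terms and one set of clocks, identically in Sections K and M.
- State once whether clinicians contact the patient after an alert, and use that statement in Sections D and K.

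No threshold, reporting scope or clinical rule is proposed here; those are for the investigators. The cost is protocol wording and possibly a small change to the app's alert logic, with no effect on sample size, endpoints or analysis.
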